### **3.5.3 Objective3**

Sample size calculation based on the objective 1 related to the of guide on the miniscrew implantation. In a previous study the response within each subject group was normally distributed with standard deviation 0.12mm(Janson G, et al.,2013). If the true difference in the experimental and control means is 0.66, the research will need to study 10 experimental subjects and 10 control subjects to be able to reject the null hypothesis that the population means of the experimental and control groups are equal with probability (power) 0.8. The Type I error probability associated with this test of this null hypothesis is 0.05. The effective size is 1.3929508.

### **3.5.4 Objective 4**

Sample size calculation based on the objective 1 related to the of guide on the miniscrew implantation. In a previous study the response within each subject group was normally distributed with standard deviation 0.02 um(Talaat S., et al.,2017). If the true difference in the experimental and control means is 0.54, the research will need to study 6 experimental subjects and 6 control subjects to be able to reject the null hypothesis that the population means of the experimental and control groups are equal with probability (power) 0.8. The Type I error probability associated with this test of this null hypothesis is 0.05. The effective size is 1.799001.

Thus, a total sample size for this study will be 24 (12 for experimental and control group) after considering 20% drop-out.

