### **3.5 Sample size calculation**

Sample size were determined using power and sample size calculation software (version 3.1.9.7) (Dupont and Plummer 1990). Since the sample size calculated for other objectives gave less number of subjects in each group, therefore the sample size selected in this research is based on objective of miniscrew implantation. The given below are the categorization as per objective.

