#### **3.5.1 Objective 1**

Sample size calculation based on the objective 1 related to the of guide on the miniscrew implantation. In a previous study the response within each subject group was normally distributed with standard deviation 1.82437mm([name],Song Hui and Xiaofeng Huang,2022). If the true difference in the experimental and control means is 2.7403, the research will need to study 8 experimental subjects and 8 control subjects to be able to reject the null hypothesis that the population means of the experimental and control groups are equal with probability (power) 0.8. The Type I

error probability associated with this test of this null hypothesis is 0.05. The effective size is 1.5451013.

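### The derivation of the total of 24 in section 3.5 contradicts itself on the governing objective, the number per group, the drop-out inflation and objective 1's effect size

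*Protocol*

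**What the plan says.** Section 3.5 of the protocol bases the sample size on the objective of miniscrew implantation and gives the reason: "Since the sample size calculated for other objectives gave less number of subjects in each group". The four calculations follow.

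- **Objective 1 (3.5.1)** assumes data "normally distributed with standard deviation 1.82437mm" and continues "If the true difference in the experimental and control means is 2.7403". It asks for 8 per group at power 0.8 and type I error 0.05, and adds: "The effective size is 1.5451013".
- **Objective 2 (3.5.2)** states 8 per group.
- **Objective 3 (3.5.3)** gives a standard deviation of 0.12 mm, a difference of 0.66 and an effect size of 1.3929508, and says that "the research will need to study 10 experimental subjects and 10 control subjects".
- **Objective 4 (3.5.4)** states 6 per group at an effect size of 1.799001.

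Section 3.5.4 then closes with the total: "Thus, a total sample size for this study will be 24 (12 for experimental and control group) after considering 20% drop-out". It does not say which number per group was inflated, or by what formula. Sections 3.6 and 3.10 carry the 24 (12 and 12) forward into randomisation and grouping.

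**The concern.** The reason given for choosing the governing objective is that it demands the most subjects. On the protocol's own figures objective 1 does not: objective 3 demands two more per group. The total cannot be traced to objective 1's stated number, and it can be traced to objective 3's only through an inflation that does not correspond to 20% loss. Objective 1's effect size also does not follow from the difference and standard deviation printed beside it.

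This is the protocol's only justification of its size. A reader cannot tell from it which comparison the trial was sized for, how many completers that comparison needs, or how much loss it can absorb.

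**Working it through.** **Inputs.** All come from sections 3.5 to 3.5.4: the stated numbers per group (8, 8, 10, 6), the effect sizes, the differences and standard deviations, type I error 0.05, power 0.80, drop-out 20% and the total of 24. Two assumptions are needed. The test is taken as two-sided, because sidedness is not stated and the null is that "the population means of the experimental and control groups are equal with probability (power) 0.8" can be rejected in either direction. Each difference is taken to be in the same unit as its standard deviation, because the differences carry no unit.

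**Step 1: reproduce the stated numbers per group.** Two-sample t test, noncentral t with 2n − 2 degrees of freedom and noncentrality d·√(n/2). The smallest n with power of at least 0.80 at each printed effect size is:

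| Objective | Printed d | Two-sided t | Power at that n | Stated n | One-sided t | Two-sided normal approximation |
|---|---|---|---|---|---|---|
| 1 | 1.5451013 | 8 | 0.819 | 8 | 6 | 7 |
| 3 | 1.3929508 | 10 | 0.838 | 10 | 8 | 9 |
| 4 | 1.799001 | 6 | 0.801 | 6 | 5 | 5 |

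Of the three methods, only the two-sided t test returns all three stated numbers, which supports the assumption on sidedness.

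**Step 2: check the effect sizes against their own inputs.**

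- Objective 1: 2.7403/1.82437 = 1.502, against a printed 1.545. At 1.502, power is 0.798 with 8 per group and 0.849 with 9. The exact solution for 80% is n = 8.04, so 9 per group.
- Objective 3: 0.66/0.12 = 5.5, against a printed 1.393.

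**Step 3: apply the drop-out.** To keep n completers after 20% loss, enrol n/(1 − 0.20).

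| Base n per group | n/0.8, rounded up | Total | n × 1.2, rounded up | Total |
|---|---|---|---|---|
| 8 (objective 1, stated) | 10 | 20 | 9.6 → 10 | 20 |
| 10 (objective 3, stated) | 12.5 → 13 | 26 | 12 | 24 |
| 9 (objective 1, from its difference and SD) | 11.25 → 12 | 24 | 10.8 → 11 | 22 |

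Inflating objective 3 on the total instead gives 20/0.8 = 25. The stated 8 does not reach 24 under either formula. The stated 10 reaches it only under multiplication by 1.2.

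**Step 4: what 12 per group leaves.** 12 × 0.8 = 9.6 per group, or 24 × 0.8 = 19.2 overall. Ten of 12 are kept only if at most 2/12 = 16.7% are lost. For objective 1 at d = 1.502, power is 0.869 with 10 against 9 completers and 0.849 with 9 against 9.

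**The case against.** Four things can be said for the protocol.

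1. **24 can be defended.** Objective 1's difference and standard deviation give 9 per group, and 9/0.8 rounds up to 12. This stands. A reader might infer that 24 cannot be obtained from objective 1 at all, and that would be wrong. What fails is the printed chain, which states 8 and not 9.

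2. **The governing objective may be mislabelled rather than wrongly chosen.** Sections 3.5.1 to 3.5.4 all open by describing themselves as the calculation for objective 1, evidently copied text. If the calculation giving 10 per group governs, it is true that the others (8, 8, 6) gave fewer. This is possible, though section 3.5 points more naturally to objective 1. It would also leave the wrong inflation in place and rest the trial on an effect size that its own inputs contradict (1.393 against 5.5).

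3. **The discrepancies are small.** Power of 0.798 rounds to the stated 0.8, and correct inflation of 10 per group moves the total only from 24 to 25 or 26. This stands, and it limits the size of the point.

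4. **Power survives drop-out.** A reader might infer that the trial falls materially short of 80% once 20% are lost. The documents do not support that. Objective 1 keeps about 0.85 to 0.87. Objective 3, taken at its printed effect size, would lie within about two points of 0.80 on either side, and that effect size is itself in doubt.

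**Conclusion.** The point holds as an internal contradiction in the sample-size derivation. The stated reason for the governing objective conflicts with the 8 and 10 per group. Objective 1's stated 8 leads to 20, not 24. Objective 3's stated 10 leads to 12 only by an inflation that is too small for 20% loss. Objective 1's effect size is 1.502 on its own inputs, not 1.545, which moves its requirement from 8 to 9 per group.

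The size is modest: one subject per group for objective 1, and one or two in the total if objective 3 governs. No material loss of power is claimed, and the enrolled number need not change. The figures rest on a two-sided t test at 0.05, equal allocation, and differences in the same unit as their standard deviations. Objective 3's power cannot usefully be quoted until its effect size is settled.

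**What to change.** Reword section 3.5, keeping 24 participants:

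- Name objective 1 explicitly as the governing objective. Restate it as d = 2.7403/1.82437 = 1.502, two-sided t test, 9 per group, power 0.85.
- Show the inflation: 9/(1 − 0.20) = 11.25, so 12 per group and 24 in total.
- Delete the claim that all other objectives gave fewer subjects.
- State that 12 per group preserves objective 3's stated 10 only up to 16.7% loss.
- Reconcile objective 3's effect size (1.393) with its difference and standard deviation (5.5) before quoting any power for it.
- Correct the copied opening sentences so that each calculation names its own objective.

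The cost is editorial, with no extra patients and no change to randomisation. The only concession is an open statement that objective 3's stated number is not fully protected against the planned drop-out.

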### **3.6 Randomization of the subjects**

The simple randomization method involves randomly assigning subjects to different groups. This means that each subject has an equal chance of being placed in any of the groups. The randomization process is typically done using a random number generator or a randomization table. This method helps ensure that the assignment of subjects to groups is unbiased and eliminates any potential selection bias. Therefore, it allows for a fair comparison between the groups and enhances the internal validity of the study.

#### **Randomization:**

**In this study, participants will be randomly assigned to either the Intervention group or the control group using a computerized random number generator.**

We will use simple randomization. Assuming 24 participants, we randomly assigned them to two groups (trial and control) of 12 participants each. The steps are as follows: generate 24 random numbers using a random number generator. Sort these random numbers. The first 12 were assigned to the intervention group and the last 12 to the control group. Ensure that participants are assigned to the corresponding group in this order.

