### **3.11 Stages of treatment**

- 1) The patient undergoes routine pre-orthodontic examination, model analysis, cephalometric measurement, and develops an orthodontic treatment plan.
- 2) .The patient undergoes routine pre-orthodontic examination, model analysis, cephalometric measurement, and develops an orthodontic treatment plan.
- 3) The process of insertion of miniscrew will be depend on the group either **Intervention** Group or **Control** Group. The guide plate will be used for miniscrew insertion in **Intervention** Group and experience based on the patient's digital films for **Control** Group. The area of insertion of the miniscrew will be the upper alveolar ridge between premolars and molar tooth. The procedure will be performed under local injection anesthesia.
- 4) The process of implanting implant nails on **Intervention** Group is as follows: the material and model of the implanted micro implant nails are exactly the same as those of the traditional positioning set. The implant nail diameter is 2mm and the length is 10 mm. The implant surgery was performed by the same orthodontist in accordance with recommended operating procedures. Preoperative local anesthesia will be performed, and micro-implant nails will be implanted at the intended

implantation site under the guidance of the guide plate. The area of implantation is maxillary zygomatic alveolar ridge.

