**5) The process of implanting implant nails on the Control Group is as follows:**

**Similar to the intervention group, but the doctor implant the miniscrew based on experience with CBCT scans.**

6) Collect date before and after implant nail implantation. The digital plaster models will be obtained by scanning with a D700 scanner (3shape, Denmark). Both digital models and CBCT scan data will be imported into Segma implant guide software (Beijing, China). The combination method is as follows: first, open the file in a way that only uses CBCT for implant design and adjust the density of anatomical landmarks such as the maxillary sinus, condylar foramen, or protrusions to an explicit level. Then, the teeth or jaw landmark points of the model and CBCT will be selected to reconstruct a 3D model.

4) The data collection will be performed by obtaining plaster model using intraoral scanner at T1(immediate post insertion) and T2 (6 months post insertion)

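### The allocation steps never link a random number to a participant before sorting; followed as written, they give a fixed 12-then-12 sequence, not a random one

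*Protocol*

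**What the plan says.** Section 3.6 opens with a general description of simple randomisation and its purpose: "This means that each subject has an equal chance of being placed in any of the groups".

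The Randomization paragraph then gives the method for this trial. Participants are allocated "using a computerized random number generator", and "We will use simple randomization". For an assumed 24 participants the listed steps are:

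1. "generate 24 random numbers using a random number generator"
2. "Sort these random numbers. The first 12 were assigned to the intervention group and the last 12 to the control group"
3. "Ensure that participants are assigned to the corresponding group in this order"

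Three other places bear on the consequence:

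- Section 3.10 puts recruitment at about two months. It also says the 24 eligible individuals will be divided into two groups at random.
- Section 3.11, step 4 (Intervention Group): "The implant surgery was performed by the same orthodontist in accordance with recommended operating procedures".
- Section 3.11, step 5 describes the control procedure as similar, except that "the doctor implant the miniscrew based on experience with CBCT scans".

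The Blinding paragraph says that those who deliver the interventions know the group assignments. The protocol does not describe concealment of the sequence before allocation.

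**The concern.** Sorting randomises only if each number carries a label, either a participant or an enrolment slot, through the sort. The labels then come out in random order and can be split 12 and 12. The listed steps mention no label. They go from drawing numbers to sorting them to naming the first and last twelve, and then tell the site to follow that order. A site that does exactly this gives the guide to the first twelve people and freehand placement to the next twelve.

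Two things would be lost. The first is the equal chance of either arm, on which the description as a randomised trial in section 3.1 depends. The second is unpredictability: anyone who knows the rule knows every coming assignment.

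A block of guided cases followed by a block of freehand cases would also tie the comparison to time. The control procedure relies on the operator's experience, so a change in skill over the series could appear as an effect of the guide. Specific objectives 1 to 3 (accuracy, stability, safety) are all comparisons between these two arms.

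**Working it through.** **The plan's own figure.** The steps use 24 participants, 12 per arm. Section 3.5.3 gives the largest requirement, 10 per arm. A two-sided t-test at 0.05 with the stated effect size 1.3929508 does give 10 per arm (power 0.838). Adding 20% gives 10 × 1.2 = 12 per arm, 24 in all. (Dividing by 0.8 would give 12.5, so 13, but that does not bear on this point.) The allocation steps have no numerical claim of their own to reproduce.

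**The steps, traced under both readings.** Let U1 to U24 be the numbers drawn.

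- *No link.* Sorting gives ranks 1 to 24. Ranks 1–12 are intervention and 13–24 control, whatever the values of U. Assigning participants in this order makes participant k intervention if k ≤ 12. There is one possible sequence.
- *Number Uk attached to slot k first.* Slot k is intervention if Uk is among the 12 smallest. There are C(24,12) = 2,704,156 equally likely sequences, and all-guide-first has probability 1/2,704,156 = 3.7 × 10⁻⁷.

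The text contains the draw, the sort, the split and the instruction to follow the order. It contains neither the attachment of numbers to slots nor a return to slot order.

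**How closely arm and order would be tied under the first reading, if surgery follows enrolment order.**

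- Mean case position: (1+12)/2 = 6.5 for the guide and (13+24)/2 = 18.5 for control, 12 cases apart.
- SD of positions 1 to 24: √((24² − 1)/12) = 6.92.
- Correlation of arm with position, in absolute value: 12 × 0.5 / 6.92 = 0.87.
- Variance inflation of the arm effect if a straight-line trend is fitted: 1/(1 − 0.87²) ≈ 1/(1 − 0.75) = 4.

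The arms share no case positions, so any adjustment would rest on an assumed trend shape.

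**Illustration only.** The documents give no learning curve. Assume that the operator's deviation falls linearly by T standard deviations over the 24 procedures, equally in both arms, with no true guide effect. The false difference is 12 × T/23 = 0.522T. The mm column uses the SD of 1.82437 mm in section 3.5.1. Type I error is from 40,000 simulated trials analysed by t-test.

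| Assumed total fall T (SD) | False difference (SD) | In mm | Type I error, 12-then-12 |
|---|---|---|---|
| 0.25 | 0.13 | 0.24 | 0.061 |
| 0.5 | 0.26 | 0.48 | 0.096 |
| 1 | 0.52 | 0.95 | 0.227 |
| 2 | 1.04 | 1.90 | 0.650 |

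Under a true random permutation the same assumed trends give a bias of about zero and a type I error of 0.048 to 0.053. With improvement over time, control cases come later and look better, so the bias runs against the guide. Fatigue or drift would reverse it.

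**The case against.** The strongest reply is that the paragraph is shorthand for a standard and valid rule: one number per participant, sort, split in half. There are as many numbers as participants. Sections 3.6 and 3.10 both say the participants are divided at random, and the literal reading makes the first step pointless. The instruction about order could mean the order of participants after sorting by their numbers. This reading is plausible, and under it there is no bias from the sequence. It does not dispose of the point, because the protocol sets out the operative steps and leaves out the one that makes them random. No other section supplies it.

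The rest of the reply limits what may be claimed, and it stands:

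- A reader might infer that all guided surgery will come first. The protocol does not say that participants are allocated one by one or that surgery follows enrolment order. Starting from 24 participants, and the pairing in the Matching paragraph, fit allocation of a known pool at least as well.
- A reader might infer that one operator for both arms is a stated fact. It is stated for the intervention arm and only implied for control.
- A reader might take the Blinding paragraph to show that the operator knows the next assignment. It says only that those delivering treatment know the groups, which a physical guide makes unavoidable. Predictability comes from the literal sequence, not from that paragraph.
- Any figure for operator trend is an assumption. An equal slope in both arms is another, since a guide may reduce reliance on experience.

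**Conclusion.** The point holds as a defect in a stated rule. Followed as written, the steps give one fixed and predictable sequence and contradict the equal chance promised in the same section. That conclusion rests on the text alone.

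Confounding of arm with time is conditional. It needs the literal reading, allocation and surgery in enrolment order over the roughly two months of recruitment, and the same orthodontist in both arms. If all hold, arm and case order correlate at 0.87, and separating them depends wholly on an assumed trend shape. The size of any bias is unknown, and the table above only shows how it would scale.

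It would go too far to conclude that the trial is not randomised, that no analysis could separate arm from time, or that objectives 1 to 3 cannot be answered. A valid reading exists, and a trend could be modelled at the price of a strong assumption and about four times the variance. The wording should still be corrected before the first allocation, because a non-random sequence cannot be undone once patients have been treated.

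**What to change.** Replace the steps in the Randomization paragraph of section 3.6 with the following:

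1. Number the enrolment slots 1 to 24 and attach one computer-generated random number to each.
2. Label the slots holding the 12 smallest numbers intervention and the other 12 control.
3. Restore the list to slot order.
4. Keep the list from the operator and from the staff who enrol participants. Reveal each assignment only after consent and baseline records are complete.

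Delete the sentence telling the site to assign participants in the sorted order. If allocation has already begun, record how the numbers were in fact linked to participants.

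The cost is a few sentences in one section and someone outside enrolment and surgery to hold the list. It needs no extra patients or visits, the 12 and 12 split is unchanged, and treatment is not affected.

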**Matching:**

To control for potential confounding variables, participants will be matched based on key characteristics such as age, gender, and baseline health status. The study involves comparing treatment outcomes in two groups, participants will be paired so that each pair consists of individuals with similar baseline characteristics.

**Blinding:**

The study will employ a particular-blind design to minimize bias. The participants and the researchers administering the interventions will be aware of the group assignments. And the researchers who interact with participants and collect data will be unaware of group assignments. This blinding helps to prevent expectations or biases from influencing the outcomes and ensures that the study results are more reliable.

### **3.7 Sample frame**

#### **3.7.1 Inclusion criteria**

- (1) The orthodontic clinical design should include the use of miniscrews for anchorage requirements in maxillary arch.
- (2) Age of 18-35 years old

(3) Patients must have no prior history of orthodontic treatment and must have a healthy periodontal condition or no history of trauma before the current orthodontic treatment.

### **3.7.2 Exclusion criteria**

- (1) Patient with poor oral hygiene, history of systemic diseases and metal allergies;
- (2) Patients with osteoporosis and inability to retain the TAD;
- (3) Patients who require orthognathic surgery for severe skeletal malocclusion;
- (4) Smoking patients which will affect the success rate of the implant placement
- (5) Patients with incomplete medical records.

